### ***Biostatistical Justification***

The difference in the corticomotor excitability (as measured by the amplitude of the motor evoked potentials (MEPs)) can be used to determine if there is a difference between the active and sham protocols. Under the conditions that the true difference between the active and sham protocols is 5% of the normalized MEP with a standard deviation of 9%, and that the correlation between the differences within an individual is 0.5, ten nonimpaired subjects will be needed to achieve at least 80% power using a two-sided test of the overall mean using a repeated measures model. The Type-I error rate was set at 0.25 for this analysis.

In our **future research**, we will design neuromodulation techniques that promote neuroplasticity to increase muscle strength and function in individuals with SCI or post-stroke. The goal of our larger project, to be submitted as an R01 application to National Center for Medical Rehabilitation Research (NCMRR) within the Eunice Kennedy Shriver National Institute for Child Health and Human Development (NICHD) in June 2020, is to determine the effect of neuroanatomy and intermittent theta burst stimulation on corticomotor excitability, and clinical scores of function in individuals with tetraplegia. This larger project will include development of a computational framework to model hysteretic effects of iTBS using participant specific MRI in order to more definitely determine the effect of brain anatomy on the efficacy of iTBS. This larger project aligns with two research priorities within NCMRR: 1) to explore multimodal approaches that promote plasticity and sensorimotor function, particularly the combination of physical therapy with stimulation treatments, and 2) to develop objective measures that may predict rehabilitation treatment response, monitor functional progress, and tailor interventions to the individual abilities, needs, and resources of the person with disabilities.

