### **Transcranial Magnetic Stimulation in Human Subjects**

Subjects who underwent MR imaging, will also participate in two sessions of TMS. Each TMS session will consist of baseline measures of MEPs in response to single pulse TMS, followed by the iTBS protocol. One iTBS session will target the biceps, and one session will target the FDI. Each session will consist of active iTBS applied to the hotspot of the target muscle, and sham iTBS. Sessions will be separated by at least 3 days to minimize the potential for carry over effects. Before and 10, 20 and 30 minutes after each iTBS session, MEPs will be recorded in order to quantify corticomotor excitability similar to our preliminary work.

Subjects will be instrumented with surface electromyography (EMG) electrodes on their dominant arm after the skin is shaved and cleaned with alcohol wipes. Surface EMG electrodes (disposable Ag-AgCl, Noraxon) will be located over the biceps and the FDI. EMG signals will be amplified (x1000) and bandpass-filtered prior to A/D conversion (CED Micro 1401 MkII, Cambridge Electronic Design). All EMG data will be sampled at 2 kHz using Spike2 software (Cambridge Electronic Design) and stored on a personal computer for offline analysis.

Prior to the iTBS session, the maximal compound muscle action potential (Mmax) will be recorded from the target muscle (biceps or FDI). The amplitude of Mmax is required to normalize MEP amplitudes.

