To record Mmax, single pulse electrical stimuli, 0.2 ms pulse width will be delivered to Erb's point via a bipolar stimulating electrode (0.47 cm^2; 2.5 cm inter-electrode distance) connected to a constant current stimulator (DS7AH, Digitimer Ltd.). To determine RMTs and record MEPs, single pulse TMS will be delivered to the motor cortex contralateral to the resting target arm using a Super Rapid Plus stimulator via a 70 mm figure-of-eight coil. The vertex at the intersection of the inion-nasion and inter-aural lines will be marked on a linen cap tied snugly on the subject's head. The coil will be held tangentially on the scalp via a support stand with the coil center rotated to induce a posterior-to-anterior cortical current across the central sulcus. The hotspot for the target muscle will be identified as the location evoking the largest peak-to-peak amplitude MEP using the lowest stimulation intensity. Resting motor threshold (RMT) will be determined as the lowest stimulus intensity that induces MEPs of  $\geq 50 \mu\text{V}$  in at least 5 of 10 consecutive stimuli with the target muscle fully relaxed. The stimulus intensity for ensuing single pulse MEP trials will be set at 120% of RMT. To record MEPs, the stimulator will be triggered to deliver 15 stimuli at a rate of 0.2 Hz. Active motor threshold (AMT) will then be determined during sustained contractions of 20% the subject's maximum effort. With visual feedback provided relative to their maximum EMG root mean squared value, subjects will sustain a 20% maximum effort contraction of the target muscle during which AMT will be determined as the stimulus intensity that elicits a MEP  $\geq 200 \mu\text{V}$  in at least 5 of 10 consecutive stimuli.

**Fig. 4.** The biceps and FDI will be targeted for the iTBS protocol in nonimpaired subjects. All subjects will be seated with the arm supported against gravity in the horizontal plane. The intensity of all iTBS pulses will be 80% of the subject's active motor threshold (AMT). Before each iTBS session (iTBS 1 and 2, which are sham and active, respectively), RMTs and motor evoked potentials (MEPs) will be recorded. MEPs will also be recorded at 10 minute intervals following iTBS.

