#### **Data and Statistical Analysis**

We will calculate the root mean square (RMS) amplitude of the evoked response, the RMS amplitude of the pre-stimulus background EMG (over a duration of approximately 25 ms matched to the

duration of the corresponding evoked response), and the peak-to-peak amplitude of the evoked response (MEP or M-wave) using purpose-written Matlab code (The MathWorks, Inc.). Stimulus events where the pre-stimulus RMS amplitude is larger than the evoked response, or where voluntary activity is detected, will be discarded to ensure similar levels of background activity across subjects and trials. MEP amplitudes will be normalized by their corresponding Mmax amplitudes. All patient characteristics, including RMTs and AMTs, will be summarized using means and standard deviations. The overall mean and standard deviation of MEPs (normalized to Mmax and unnormalized) will be reported. Linear mixed effect models will be used to determine the overall mean difference between the normalized MEP amplitudes between the active and sham protocols. Separate mixed effect model analyses will be used for each muscle (biceps and FDI), condition (sham and active) and time point following iTBS (in total 12 mixed effect models). Since this is a pilot study, all inference will be performed at the 0.25 level and no adjustment for multiple comparisons will be made. Pearson correlation coefficients will be computed to test for correlations between mean MEPs in response to single pulse TMS (before iTBS protocol) and the maximum induced electric field. A strong correlation between MEPs and induced electric fields would indicate a strong relationship between our experimental and computational outcome measures and provide a foundation for our future work. Pearson correlation coefficients will also be computed to test for correlations between mean MEPs following iTBS and maximum induced electric fields to determine whether greater induced electric fields indicate a participant is more responsive to the iTBS protocol.

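### The 80% power is for a repeated-measures test of the overall active-sham mean, but the 12 planned models are split by time point and condition, so none performs that test

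*Combined protocol and SAP*

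**What the plan says.** The Biostatistical Justification assumes that "the true difference between the active and sham protocols is 5% of the normalized MEP with a standard deviation of 9" per cent, and that "the correlation between the differences within an individual is 0.5". From these it concludes that "ten nonimpaired subjects will be needed to achieve at least 80% power using a two-sided test of the overall mean", using a repeated-measures model with a Type I error rate of 0.25. It does not say what the repeated differences are or how many each person contributes.

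The Data and Statistical Analysis section states the same target: "Linear mixed effect models will be used to determine the overall mean difference between the normalized MEP amplitudes between the active and sham protocols". The next sentence calls for separate analyses for each muscle, "condition (sham and active) and time point following iTBS (in total 12 mixed effect models". All inference is at the 0.25 level with no multiplicity adjustment.

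The section Transcranial Magnetic Stimulation in Human Subjects gives the measurement schedule: "Before and 10, 20 and 30 minutes after each iTBS session, MEPs will be recorded". At each recording "the stimulator will be triggered to deliver 15 stimuli at a rate of 0.2 Hz". The plan does not say whether the 15 single responses or their average enter the models.

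**The concern.** The sample size rests on one kind of test and the model list describes another. The powered test combines several correlated active-sham differences per person into one overall mean. The listed models are split by time point, so none combines the three post-iTBS measurements. They are also split by condition, so on a literal reading no model holds both active and sham data and none can estimate the difference between them.

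The analyst would have to decide how to form the main comparison, possibly after seeing the data. With alpha at 0.25 and no multiplicity adjustment, the choice between one pooled test and three time-specific tests per muscle affects both the error rates and the meaning of a positive result. If the comparison is made time point by time point on subject-level averages, the plan's own inputs no longer support the 80% claim.

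**Working it through.** **Counting the models.** Two muscles × two conditions × three post-iTBS time points = 12, the total the plan prints. Had both conditions been inside each model, the count would be 2 × 3 = 6. The printed total therefore fits only if condition and time point are both splitting variables.

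**Inputs** (all from the Biostatistical Justification): difference 5, SD 9 (read as the SD of one active-sham difference), correlation 0.5 between differences within a person, two-sided alpha 0.25, n = 10. If 9 were instead the SD of each measurement with active-sham correlation 0.5, the SD of the difference would be 9 × √(2 − 2 × 0.5) = 9, the same value.

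**Method.** For the mean of k differences per person,

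SD(k) = 9 × √[(1 + (k − 1) × 0.5) / k].

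Power comes from a one-sample t test on these means: noncentral t, 9 degrees of freedom, noncentrality 5 × √10 / SD(k), critical value 1.230. The normal approximation uses 1.150.

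**Reproducing the plan's figure.** Take k = 3, the three post-iTBS time points. This is an assumption, because the repeats are not stated.
- SD(3) = 9 × √(2/3) = 7.35; noncentrality 5 × 3.162 / 7.35 = 2.15.
- Power is 82.2% at n = 10 and 79.0% at n = 9. Ten is the smallest number reaching 80%, so the stated sample size reproduces under pooling over time.

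**A single time point.** With k = 1 and one averaged value per condition per person:
- SD(1) = 9; noncentrality 5 × 3.162 / 9 = 1.76.
- Power at n = 10 is 70.8% (73.0% by normal approximation).
- n = 13 gives 78.8% and n = 14 gives 81.0%, so 14 subjects are needed for 80%.
- The difference detectable with 80% power at n = 10 is 5.9, against 4.8 for k = 3.

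**Range over the unstated number of repeats:**

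| Repeats k | SD of mean | Power at n = 10 (t) | Power at n = 10 (normal) | Smallest n for 80% (t / normal) |
|---|---|---|---|---|
| 1 | 9.00 | 70.8% | 73.0% | 14 / 13 |
| 2 | 7.79 | 78.9% | 81.1% | 11 / 10 |
| 3 | 7.35 | 82.2% | 84.2% | 10 / 9 |
| 6 | 6.87 | 85.6% | 87.5% | 9 / 8 |
| 15 | 6.57 | 87.8% | 89.6% | 8 / 7 |

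Two repeats (for example the two muscles) also give ten under the normal approximation, but the models are split by muscle as well, so the mismatch remains. Fifteen repeats (the single-pulse trials at one time point) would need only 8 subjects and so do not explain ten. For the 12 models taken literally, no power for the active-sham difference can be defined.

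**The case against.** The strongest reply is that the 12 models need not be the whole analysis. The sentence before the list names the overall active-sham difference, which is what was powered. The 12 could be additional within-condition analyses, such as each post-iTBS time point against the baseline responses, where splitting by condition makes sense. The plan would then be under-specified rather than contradictory. That reading is not excluded, but neither is it written down, and it would still leave the powered model with no stated terms, repeats or contrast.

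A second reply is that 71% belongs to a scenario the plan does not describe: both conditions in each model, and one averaged value per condition. A mixed model at a single time point suggests trial-level data, and with 15 trials as repeats power is 88%. This stands in part. The 71% is conditional on subject-level averages and should be quoted that way. But trial-level data would not put the active-sham contrast into a model that holds only one condition.

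A third is that 82% is a reconstruction, since two repeats also lead to ten under the normal approximation. That is correct about where ten came from. It does not affect 82% as the t-based power, on the plan's inputs, of a contrast averaged over three time points.

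Finally, this is a ten-person pilot with lenient alpha. That limits the consequences, but the plan chose to justify its size formally, and the justification should match the analysis.

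**Conclusion.** The concern holds. The stated power belongs to a test of the overall active-sham mean that the analysis section names but does not specify. None of the 12 listed models pools the time points and, read literally, none contains the contrast. The number ten is not itself wrong: it reproduces at 82% power if three time points are averaged.

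If the comparison is made at single time points on subject-level averages, the chance of missing a true 5-point difference is about 29% per test, against 18% for the three-time-point average. These figures take 9 as the SD of one active-sham difference and 0.5 as the common correlation between repeats. The 18% also assumes three repeats. The mismatch between the powered test and the listed models depends on none of these assumptions. It should be fixed, but it does not threaten the sample size.

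**What to change.** For each muscle, specify one repeated-measures mixed model that contains both conditions and all three post-iTBS time points, with the active-minus-sham contrast averaged over time as the main test and time-specific contrasts secondary. State what the repeats behind the power calculation are; for a contrast over the three time points, the plan's inputs give 82% at n = 10. State whether trial-level or averaged responses enter the model. If the 12 models are meant as additional within-condition analyses, say so and describe them separately.

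If time-specific tests are to remain primary, put both conditions in each model, correct the count to six, and restate power as about 71% per test, conditional on subject-level averages.

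The cost is SAP wording. No extra subjects or measurements are needed. Keeping time-specific tests as primary means reporting a less favourable power.

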### **Potential Risks**

Transcranial magnetic stimulation (TMS) is a non-invasive brain stimulation technique. TMS protocols, including the single pulse and intermittent theta burst stimulation protocols that we propose to use in human subjects, present non-significant risk to the health, safety, or welfare of a human subject. The risks associated with TMS protocols have been investigated and discussed in detail. Risks and side effects associated with TMS include: heating, induced voltages, forces and magnetization, effect on hearing, induced seizure or syncope, headache, local pain or discomfort, and neurophysiological changes.

The risk of heating includes the overheating of the stimulating coil and/or brain tissue. This risk will be minimized by using a Magstim Double 70mm Air Film Coil. The Double 70mm Air Film Coil contains two temperature sensors. When the internal coil temperature approaches 20°C, indicators on the UI illuminate. When the internal temperature reaches 41°C, the stimulator will shut down and the Replace Coil Light will illuminate.

The risks of induced voltages, forces and magnetization will be minimized by screening to exclude individuals with implanted devices. Our protocols will exclude the use of TMS on, or in the vicinity of, patients or users with cardiac demand pacemakers, implanted defibrillators and/or implanted neurostimulators.

The effect on hearing will be minimized by providing ear plugs to all participants.

The risk of induced seizure or syncope will be minimized by screening procedures to exclude individuals taking medications that lower the threshold for inducing seizures. Intake of or withdrawal from certain central nervous system (CNS) active drugs lowers seizure threshold. The actual risk for seizure induction may depend on additional, not yet fully explored, factors such as drug dose, speed of dose increase (or decrease), and combination with other CNS active drugs. The majority of reported TMS-induced seizures have occurred in subjects/patients on drugs with seizure threshold lowering potential. Thus, we will exclude individuals taking medications as listed in section 5.3 of the report by Rossi et al.

